9.7.1.4 Handling of Missing values

For the primary analysis, resulting missing values will be replaced using MI procedure (like a hypothetical strategy in the estimand framework). The data will be separated into two subsets based on the treatment groups which will ensure that the imputation process accounts for potential difference between these

Document Title:	Statistical Analysis Plan		
Version Number:	Final 1.0	Date:	18Oct2024
Protocol Number:	SARO.17.009	Sponsor Name:	Zydus Therapeutics INC

groups. Complete dataset will be generated using PROC MI and recombine the data set for subsequent analysis. The number of imputed data set should be sufficient to ensure reliable result. The number of imputations (m) may be determined using fraction of missing information and the percentage of missing data. Generally, 5 to 20 imputations are required to perform to ensure robust result. A productive mean approach or regression method can be used for the imputation. PROC MIANALYZE will be used to combine the results of complete dataset results.

9.7.1.5 Sensitivity Analysis

In order to test robustness of results following analyses will be performed:

- Change in hepatic fat content from baseline to Week 24 will be analyzed using analysis of covariance (ANCOVA) model for PP population. No missing values will be imputed for the analysis.
- Change in hepatic fat content from baseline to Week 24 will be analyzed using analysis of covariance (ANCOVA) model for mITT population, where missing values will be imputed as per above strategy.

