8.4 Handling of Dropouts and Missing data

Clarifications, wherever possible, will be obtained from the respective Investigator or data management team for any missing data or for any illegible entry, unused or unauthenticated data and this will be recorded in the data handling report (If required) before the final database lock.

Dropouts and missing values, considering missing values as missing at random (MAR) will be imputed by using multiple imputation method for primary efficacy variable, for mITT population only, and will be considered as supportive to the analysis.

Dropouts and missing values will not be imputed for safety and secondary endpoints.

Imputed data should be flagged and properly footnoted as “imputed”. Title should indicate that imputed data is used for summary.

Adverse events with unknown end date/time will be counted as an ongoing AEs, if ongoing is ticked on the CRF. Medications with unknown end date/time will be considered as concomitant. Adverse events and medications with partially missing start or end dates will be considered ongoing and concomitant respectively unless the non-missing portion of the dates definitively proves otherwise.

Document Title:	Statistical Analysis Plan		
Version Number:	Final 1.0	Date:	18Oct2024
Protocol Number:	SARO.17.009	Sponsor Name:	Zydus Therapeutics INC

Partial dates for Adverse events and medications will be imputed as follows for derivation of treatment emergent and Prior/Concomitant flags respectively:

- Missing day in start date of a time period is imputed by the first day of the month.
- Missing day in end date of a time period is imputed by the last day of the month.
- Missing month in start date of a time period is imputed by January of the year.
- Missing month in end date of a time period is imputed by December of the year.
- Missing year is not imputed.
- After above imputation if start or end date is after Participant's end of study date then start or end date is set to Participant's end of study date.

If required, time will be imputed in the following way:

Times should be printed in the format "HH:MM". "HH" represents the 2-digit hour portion of the time. "MM" represents the 2-digit minute portion of the time. Both hour and minute portions of time are zero padded integer values. Missing time portions should be represented on Participant listings as dashes ("10:--" and "--:--").

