9.7.1.3 Analysis Strategy

Primary analysis will be primarily based on the PP population and analysis, based on mITT population with missing value imputation for primary endpoint will be considered as supportive analyses.

The primary efficacy endpoint in this study is the change in hepatic fat content from baseline following 24 weeks of treatment measured by MRI-PDFF. The change from baseline of hepatic fat will be determined as (Visit 8 [Week 24] value – Baseline value).

The actual values observed and change from baseline values of hepatic fat content will be summarized using the number of non-missing observations (n), mean (Mean), standard deviation (SD), median, minimum (Min) and maximum (Max) by treatment groups for baseline and scheduled all visits (i.e. baseline to Week 24 visits).

To check the mean significance difference between baseline and scheduled visit for Week 24, a paired t-test at 5% level of significance will be used.

Following sample SAS code will be used for paired t-test:

```
proc ttest data=data sides=2 alpha=0.5;
paired BASE*AVAL;
run;
```

Where AVAL: variable with post baseline value; BASE: variable with baseline value.

Document Title:	Statistical Analysis Plan		
Version Number:	Final 1.0	Date:	18Oct2024
Protocol Number:	SARO.17.009	Sponsor Name:	Zydus Therapeutics INC

The primary efficacy endpoint, the change from baseline in hepatic fat content at Week 24 will be analyzed using an analysis of covariance (ANCOVA) model. The model will include change in the hepatic fat content values from baseline as dependent variable, treatment group as a fixed effect and baseline values as a covariate.

The estimate the LS means for treatment groups and its 95% confidence interval, the difference of LS Mean for treatment group (Saroglitzaz magnesium 4 mg – Placebo) and its 95% confidence interval of the difference of LS Mean for treatment group, and p-value to check the significance difference at 5% level of significance will be generated using ANCOVA model.

The following sample SAS code pertains to the ANCOVA analysis:

```
proc mixed data=DATA;
class TRT;
model CHG = BASE TRT/solution;
lsmeans TRT/ stderr pdiff cl alpha=0.05;
ods output diffs = DIFFS lsmeans = LSMEANS;
run;
```

Where, CHG: variable with change from baseline values; BASE: variable with baseline values; TRT: variable with treatment values.

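### The sensitivity analyses in SAP 9.7.1.5 repeat the primary and supportive analyses, and nothing planned tests departures from missing at random

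*SAP*

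**What the plan says.** SAP section 9.7.1.3 (Analysis Strategy) fixes the population: "Primary analysis will be primarily based on the PP population". The model is an ANCOVA of change in hepatic fat with "treatment group as a fixed effect and baseline values as a covariate". The same section adds a second analysis, "based on mITT population with missing value imputation for primary endpoint will be considered as supportive analyses".

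Section 9.7.1.5 (Sensitivity Analysis) begins "In order to test robustness of results following analyses will be performed" and gives two bullets. The first is an ANCOVA "model for PP population. No missing values will be imputed for the analysis". The second is an ANCOVA "model for mITT population, where missing values will be imputed as per above strategy".

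Section 8.4 supplies the missing-data assumption: values, "considering missing values as missing at random (MAR) will be imputed by using multiple imputation method". It confines this to the mITT set and calls it supportive. Section 9.7.1.4, in contrast, assigns the imputation to the primary analysis. It splits the data by treatment group before PROC MI and recombines them afterwards.

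Two definitions in section 8.2 matter here. PP requires the primary outcome at both baseline and end of treatment, compliance of 80% to 120%, and no deviation that could affect the primary outcome. mITT requires at least one post-baseline value of the primary outcome. Protocol section 7.2 lists MRI-PDFF among the Week 24 assessments and not among those at Week 12.

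**The concern.** A sensitivity analysis is useful when it changes an assumption on which the main result depends. Here the section set aside for that purpose appears to list the main and supportive analyses again.

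The assumption the data cannot check concerns women with no Week 24 scan, including any taken off drug for safety under protocol section 4.5. Their liver fat may not have followed the course of women in the same arm who were scanned. If the treatment effect depends on how these women are handled, neither bullet would show it. With recruitment closed at 60 and the plan itself expecting 20% loss, about 12 of 60 women could be affected.

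**Working it through.** **Step 1. Compare the analyses attribute by attribute.**

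| | Set | Model | Missing values |
|---|---|---|---|
| Primary (9.7.1.3) | PP | ANCOVA: treatment, baseline | None possible; both scans required (8.2) |
| Bullet 1 (9.7.1.5) | PP | ANCOVA | None imputed |
| Supportive (9.7.1.3) | mITT | ANCOVA: treatment, baseline | Multiple imputation, missing at random |
| Bullet 2 (9.7.1.5) | mITT | ANCOVA | Same multiple imputation |

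Rows 1 and 2 are one analysis; rows 3 and 4 are another. Reading 9.7.1.4 as imputing the primary analysis changes nothing for bullet 1, because PP data are complete.

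**Step 2. Ask whether each bullet can disagree with the primary result.** I used 2,000 simulated trials per scenario: 30 per arm, assumed effect 4 and SD 6, ANCOVA with baseline, 20 imputations by arm.

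- Bullet 1 differed from the primary in 0 of 2,000 trials in every scenario.
- Bullet 2, with nobody in mITT outside PP: 0% disagreement on significance at 5%.
- Bullet 2, with scanned women outside PP who were off drug (assumed no drug effect): 10.9% disagreement with 3 per arm, 17.4% with 6 per arm.
- Bullet 2, with 6 per arm unscanned but imputed by arm: mean shift in the estimate 0.003 points; 5.7% disagreement, from imputation noise and inference only.

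So bullet 2 tests exclusion from PP. It hardly tests the missing-data assumption.

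**Step 3. Ask whom the imputation would reach.** A woman with no post-baseline MRI-PDFF is outside SAP mITT. With the scan scheduled after baseline only at Week 24, a woman in mITT normally has the Week 24 value. The exception is an early-termination scan (protocol sections 4.4 and 7.2) that is not counted as Week 24. This step relies on the protocol text, since the schedule tables are not legible in the public copies.

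**Step 4. Illustrate what a departure from missing at random could do.** Inputs from the SAP: 60 recruited (taken as 30 per arm), 20% loss (6 per arm), a 9% change on saroglitazar and a 4% difference (8.5). Assumptions: these are absolute points, both are reductions, and placebo is therefore 9 − 4 = 5. The SD is also assumed. It is the value at which 37 per arm gives 80% power for a difference of 4 in a two-sided 5% t-test, which is 6.06. The printed SD of 0.6 does not fit a difference of 4: taken literally it needs 2 per arm.

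Differences, with 80% observed and 20% missing on saroglitazar:

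- Missing at random: 9 − 5 = 4.0
- Missing saroglitazar values follow placebo: 0.8 × 9 + 0.2 × 5 − 5 = 3.2
- Missing saroglitazar values show no change: 0.8 × 9 + 0.2 × 0 − 5 = 2.2

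Simulated standard errors under Rubin's rules (24 observed and 6 imputed per arm, 20 imputations) are about 1.8, 1.8 and 1.9 on roughly 40 degrees of freedom:

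- 4.0 / 1.8 = 2.22, p about 0.03
- 3.2 / 1.8 = 1.78, p about 0.08
- 2.2 / 1.9 = 1.16, p about 0.25

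For comparison, completers only: SE = 6.06 × √(2/24) = 1.75, t = 4/1.75 = 2.29, p = 0.027.

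Range by missing fraction f on saroglitazar, using 4(1 − f) for the placebo reference and 9(1 − f) − 5 for no change: at 10%, 3.6 and 3.1; at 20%, 3.2 and 2.2; at 30%, 2.8 and 1.3.

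**The case against.** Several stronger readings are tempting, and the documents do not support them.

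- **That neither sensitivity analysis could ever contradict the primary.** This is true of bullet 1 only. mITT keeps scanned women who were non-compliant or had deviations, and the protocol asks for end-of-treatment assessments where possible in women who stop early. Step 2 shows that the two sets can disagree.
- **That the SAP claims robustness, or that nothing probes it.** The SAP states an aim, and what the report will say is unknown. Section 9.7.1.2 also plans an ALT sensitivity analysis, by stratum or by covariate, and section 9.7.1.6 adds ALT and country subgroups. These address eligibility and region, not missing scans.
- **That the plan credits dropouts with the benefit seen in completers.** Under SAP mITT most unscanned women are left out, not imputed.
- **That p-values can be read off SE = 6.06 × √(2/30) = 1.56.** That treats six imputed women per arm as observed. It gives 0.013, 0.045 and 0.17, which are too small, and it puts the placebo-reference case on the wrong side of 5%.

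The no-change case is also one-sided, since placebo dropouts keep their reduction. With no change among dropouts in both arms the difference is 0.8 × 9 − 0.8 × 5 = 3.2. Finally, this is a proof-of-concept trial, and the choice among methods that depart from missing at random is partly preference. All of this narrows the point. The duplication and the lack of any such analysis remain.

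**Conclusion.** The point holds in a limited form. Section 9.7.1.5 adds no analysis to section 9.7.1.3. Bullet 1 cannot differ from the primary analysis. Bullet 2 can differ only through the women excluded from PP. No planned analysis varies the missing-at-random assumption, and most women without a follow-up scan enter no efficacy analysis of the primary endpoint.

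The duplication and the exclusion follow from the SAP's definitions and the protocol's visit text, and need no numerical assumption. The size is illustrative only. At the plan's own 20% loss, plausible alternatives move a 4.0-point difference to 3.2 or 2.2 and p from about 0.03 to about 0.08 or 0.25. Those figures rest on the assumed scale, placebo mean, SD and equal loss per arm. They do not predict the trial's result. This is a worthwhile, low-cost correction; it does not by itself invalidate the primary analysis.

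**What to change.** Replace the two bullets in section 9.7.1.5 with two analyses in all randomised and dosed women who have a baseline MRI:

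1. **Tipping point.** Impute missing Week 24 changes, then shift the imputed saroglitazar values toward no benefit in fixed, prespecified steps until the 95% CI for the treatment difference includes 0. Report the shift at which this happens.
2. **Reference-based imputation.** Draw missing saroglitazar values from the placebo model. This must run on the combined arms, because the by-arm split in 9.7.1.4 leaves no placebo model for the saroglitazar data.

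Keep the PP and mITT ANCOVAs where 9.7.1.3 already defines them. Reconcile sections 8.4, 9.7.1.3 and 9.7.1.4 so that one statement says whether imputation belongs to the primary or the supportive analysis. State also how an early-termination scan is classified.

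The cost is a new analysis set, SAP wording, modest extra programming and one or two tables, which may show a less favourable figure than the primary analysis.

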9.7.1.6 Subgroup Analysis

The primary endpoint will be analyzed separately based on the prespecified ALT scores and geographical region as subgroups, and the treatment effect estimates will be presented for each subgroups. The model used for the primary analysis will be applied within each subgroup to estimate the treatment effect. The PP and mITT populations – Imputed will be used for primary endpoint subgroup analysis.

The subgroups are defined as follows:

a) ALT Scores

- ALT values at baseline ≥ 38
- ALT values at baseline < 38

b) Geographical region (Country):

- Mexico
- USA

9.7.2 Secondary Efficacy Analysis

9.7.2.1 Endpoints

The secondary efficacy endpoints are:

1. Change from baseline in Liver Enzymes/LFTs (ALT, AST, ALP, GGT, serum protein, albumin and total bilirubin) at Week 12 and Week 24.
2. Change from baseline in Insulin resistance (IR) measured by Homeostasis Model Assessment (HOMA) at Week 12 and Week 24.
3. Change from baseline in CK-18, hs-CRP, TNF α and liver stiffness measured by transient elastography/FibroScan at Week 24.

Document Title:	Statistical Analysis Plan		
Version Number:	Final 1.0	Date:	18Oct2024
Protocol Number:	SARO.17.009	Sponsor Name:	Zydus Therapeutics INC

4. Change from baseline in controlled attenuation parameter measured by transient elastography/ FibroScan at Week 24.
5. Change from baseline in body weight, body mass index (BMI) and waist circumference at Week 12 and Week 24.
6. Change from baseline in MRI-derived total liver fat index and total liver volume at Week 24.
7. Change from baseline in serum lipid profile and lipoproteins (TG, TC, HDL, LDL, sdLDL, VLDL, ApoA and ApoB) at Week 12 and Week 24.
8. Change from baseline in Sex hormone binding globulin (SHBG) level at Week 12 and Week 24.
9. Change from baseline in ovarian function (Total testosterone, 17-hydroxyprogesterone, free testosterone, luteinizing hormone, follicle-stimulating hormone, LH-to-FSH ratio and estradiol) at Week 12 and Week 24.
10. Change from baseline in free androgen index at Week 12 and Week 24.

9.7.2.2 Analysis Strategy

The analysis for the secondary efficacy endpoints performed as below:

For the analysis of the secondary endpoints, i.e., Change from baseline in Liver Enzymes/LFTs, Insulin resistance (IR) measured by HOMA, CK-18, hs-CRP, TNF α , liver stiffness, controlled attenuation parameter, body weight, body mass index (BMI), waist circumference, total liver fat index, total liver volume, serum lipid profile and lipoproteins, sex hormone binding globulin level, ovarian function parameters and free androgen index. The analysis of covariance ANCOVA model will be applied separately at each visit as appropriate. The model will include treatment as a fixed effect and the corresponding baseline values of the endpoint as a covariate.

For each visits the estimate of the LS Means for treatment groups and its 95% confidence interval, LS Mean for treatment group difference (Saroglitzaz magnesium 4 mg – Placebo) and its 95% confidence interval of the LS Mean for treatment group difference, and p-value to check the significance difference at 5% level of significance will be generated from ANCOVA model. These analyses will provide the treatment effect at each visit while controlling for baseline differences

Descriptive summaries will be provided for all the secondary efficacy endpoints at each scheduled visit by treatment group. All secondary efficacy analysis will be conducted primarily based on the PP population and analysis, based on mITT population will be considered as supportive analyses .

9.7.3 Exploratory Efficacy Analysis

Not applicable

9.7.4 Pharmacokinetics Analysis

Pharmacokinetic analyses plan (PAP) will be prepared separately.

Document Title:	Statistical Analysis Plan		
Version Number:	Final 1.0	Date:	18Oct2024
Protocol Number:	SARO.17.009	Sponsor Name:	Zydus Therapeutics INC

9.8 Safety Analysis

9.8.1 Adverse Events

The applicable definition of an Adverse Event (AE) is any unfavorable or unintended sign, symptom or disease temporally associated with the use of study drug whether or not considered related to study drug, as per the study protocol. Treatment-emergent AEs are defined as any AE that started after the first dose of study drug or started before the first dose but increased in severity or frequency after administration of the initial dose of study drug. The period for treatment-emergent AE analysis starts from the first exposure to the study drug until the participant exits the study.

All the AEs, serious adverse events (SAEs), treatment emergent adverse event (TEAEs) and expected adverse event reported throughout the study, shall be coded and classified according to the standards of latest version of MedDRA (Medical Dictionary for Regulatory Activities) and grouped by preferred term (PT) and system organ class (SOC).

All adverse events for each participant, including the same event on several occasions should be listed for safety population giving both preferred term and original term used by the investigator.

The summary of frequency counts of the number of adverse events (E), and the number of participants with adverse events (n), and the percentages (%) for the number of participants with adverse events will be presented for treatment groups and for overall. For the summaries which count the number of participants, if a participant has more than one TEAE the participant will be counted only once in accordance with SOC and PT. When AEs occur more than once for a participant, the maximal severity (Maximum severity between severity and CTCAE Grade will be considered) and the strongest relationship to the treatment group will be counted. Safety analysis population will be used for adverse events summary tables.

In addition to an overall presentation of all TEAEs, reports will be generated for special classes of TEAEs as follows:

- Overall Summary of AEs
- TEAEs by SOC and PT
- Serious TEAEs by SOC and PT
- TEAEs leading to death by SOC and PT
- TEAEs leading to permanent discontinuation by SOC and PT
- TEAEs by SOC, PT and by Strongest Relationship to Study Drug
- TEAEs by SOC, PT and by Maximum Severity

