4.5 STOPPING CRITERIA FOR INDIVIDUAL PATIENTS

The following clinical events warrant discontinuation of study drug; however, the patient will continue to be followed for safety, hormonal profile, liver function tests and lipid levels until the event has resolved, i.e., clinical laboratory value(s) has/have returned to baseline or is/are no longer of clinical significance. Discontinuation of study drug will only occur if mandated by safety events as defined below:

Approved by: [name]	Protocol No. SARO.17.009 Version No.: 5.0
------------------------------------	--

 Zydus Discovery DMCC	CLINICAL TRIAL PROTOCOL Saroglitazar Magnesium – Phase 2A SARO.17.009	Confidential Page 44 of 82
--	---	-------------------------------

- Discontinue any patient with an adverse event of Common Terminology Criteria for Adverse Event (CTCAE) grade 3 or higher that is possible or probable drug related and discontinue any patient with an AE of CTCAE grade 4 or higher regardless of attribution to drug.
- Serious AE that may be related to the drug and warrant discontinuation as per discretion of the PI.
- In the opinion of the PI, continuation of study drug poses a health risk to the patient.
- Evidence of drug induced liver injury requiring study drug discontinuation as shown in the algorithm below.
- The second LFTs [AST, ALT, ALP, GGT, serum protein, albumin and total bilirubin (with conjugated bilirubin)] values during the Screening Phase (those obtained at Visit 2) will be considered as baseline for the safety assessment.
 - If patients with abnormal baseline liver indices develop elevations of AST or ALT greater than 2 times baseline or total bilirubin greater than 1.5 X baseline values (BL) while on study, testing should be repeated within 48-72 hours. If there are persistent elevations in ALT or AST greater than 2 X baseline or TB greater than 1.5 X baseline values, then close observation (see DILI Guidance for definition, testing and physical examination 2-3 times per week) should be initiated or drug should be discontinued.
 - A decision to discontinue or temporarily interrupt a study drug should be considered based on factors that include how much higher baseline ALT and AST were relative to the upper limit of normal (ULN) and how much the on study ALT and AST levels have increased relative to baseline, in addition to whether there is concomitant elevation of bilirubin or INR.

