4.6 TERMINATION OF THE CLINICAL STUDY

If the Investigator, the Sponsor or the Medical Monitor becomes aware of conditions or events that suggest a possible hazard to patients if the clinical study continues, then the clinical study may be terminated after appropriate consultation among the involved parties. Also, the clinical study may be terminated at the Sponsor's discretion in the absence of such a finding. Conditions that may warrant termination of the clinical study include, but are not limited to:

- The discovery of an unexpected, relevant or unacceptable risk to the patients enrolled in the clinical study;
- Three patients develop the same AE of CTCAE grade 3, considered to be at least probably related to study drug;
- Two patients develop any AE of CTCAE grade 4, considered to be at least probably related to study drug;
- One patient develops an AE of CTCAE grade 5, considered to be at least probably related to study drug;
- Failure to enroll patients at the required rate;
- A decision of the Sponsor to suspend or discontinue development of the study drug.

Should the study be terminated and/or the site closed for whatever reason, a copy of all documentation pertaining to the study and study drugs must be returned to the Sponsor. All the site specific documents will be archived at study site.

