9.4 PROCEDURES

9.4.1 Adverse Events

Adverse event reporting will begin after the informed consent has been signed and will continue until end of the study (i.e., the safety telephone call). The Common Terminology Criteria for Adverse Event (Version 4.03 or higher) system will be used for reporting and grading AEs.

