9.4.1.4 Assessment of Adverse Events

Each AE will be assessed by the PI with regard to the following categories:

Severity

Approved by: [name]	Protocol No. SARO.17.009 Version No.: 5.0
------------------------------------	--

 Zydus Discovery DMCC	CLINICAL TRIAL PROTOCOL Saroglitzaz Magnesium – Phase 2A SARO.17.009	Confidential Page 71 of 82
---	--	-------------------------------

The PI will provide an assessment of the severity of each AE by recording a severity rating on the appropriate AE reporting page of the patient's eCRF. Severity will be assessed according to the following scale:

Mild: Event is usually transient and easily tolerated, requiring no special treatment and causing no disruption of the patient's normal daily activities.

Moderate: Event introduces a low level of inconvenience or concern to the patient and may interfere with daily activities, but is usually improved by simple therapeutic measures. Moderate experiences may cause some interference with functioning.

Severe: Event interrupts the patient's normal daily activities and generally requires systemic drug therapy or other treatment. Severe events are usually incapacitating.

Causality

For all AEs, the PI will provide an assessment of causal relationship to study drug. The causality assessment must be recorded on the appropriate AE reporting page of the patient's eCRF.

Causal relationship will be classified according to the following criteria:

- Unrelated
- Possibly related: Suggests that the association of the AE with the study drug is unknown. However, the AE is not reasonably supported by other conditions.
- Probably related: Suggests that a reasonable temporal sequence of the AE with study drug administration exists and, based upon the PI's clinical experience, the association of the AE with study drug seems likely.
- Definitely related: Suggests that a causal relationship exists between the study drug and the AE, and other conditions (concomitant illness, progression or expression of the disease state, reaction to concomitant medication) do not appear to explain the AE.
- Unknown

Outcome

Outcome of AEs will be defined according to the ICH topic E2B, ICH Guideline, as follows:

- Recovered/Resolved
- Recovered/Resolved with sequelae
- Recovering/Resolving
- Not Recovered/Not Resolved
- Fatal
- Unknown

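### SAP 9.8.1 takes AE severity as the maximum of two unmapped scales, so the only severity table listed is undefined, can only err upward, and shows neither protocol scale

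*SAP*

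**What the plan says.** The protocol carries two severity systems.

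- Protocol 9.4.1 adopts CTCAE version 4.03 or higher and states that this "system will be used for reporting and grading AEs".
- Protocol 9.4.1.4 has the investigator rate every event on a separate scale: "Severity will be assessed according to the following scale", with three levels (mild, moderate, severe). The top level is defined by function and need for treatment: "Severe: Event interrupts the patient's normal daily activities and generally requires systemic drug therapy or other treatment". There is no level for life-threatening or fatal events.
- Protocol 8.4.3 plans AE incidence by severity, among other factors, within SOC and PT. The only scale the protocol defines under the name severity is the three-level one.

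SAP 9.8.1 merges the two. In a sentence that opens "When AEs occur more than once for a participant", it counts "the maximal severity (Maximum severity between severity and CTCAE Grade will be considered". The severity output in its list of TEAE tables is "TEAEs by SOC, PT and by Maximum Severity". No table by CTCAE grade alone, or by investigator severity alone, is listed. The table of differences from the protocol in SAP section 10 does not mention the merging.

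**The concern.** A maximum needs both inputs on one ordered scale. Here one has three levels and the other is used up to grade 5, with different definitions and no crosswalk. Two programmers could both follow the SAP and produce different tables.

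Safety is part of the study's stated purpose, and this is its one planned summary of how severe events were. If a count in its top row cannot be read as a number rated severe by investigators or as a number at a given CTCAE grade, the report has no severity summary on either protocol scale. The protocol itself treats grades 3, 4 and 5 as different things. Section 4.5 separates "CTCAE) grade 3 or higher that is possible or probable drug related" from grade 4 or higher with any attribution, and section 4.6 sets separate thresholds for grade 3, grade 4 and grade 5 ("One patient develops an AE of CTCAE grade 5"). A table with three rows would lose that distinction.

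**Working it through.** The plan states no figure on this point, so there is none to reproduce. The check is whether the rule is defined, which way it can err, and what the error might look like.

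**1. Is the maximum defined?** Let S be the investigator rating (3 levels) and C the CTCAE grade, taken here as 1 to 5 (the protocol names 3, 4 and 5). The SAP gives no mapping and does not say which scale labels the rows. Two readings both fit the text:

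| Event | Three rows (grade 3 or higher = severe) | Five rows (mild = 1, moderate = 2, severe = 3) |
|---|---|---|
| Severe, grade 2 | Severe | 3 |
| Moderate, grade 4 | Severe | 4 |
| Severe, grade 5 | Severe | 5 |

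The first reading collapses grades 3, 4 and 5. The second puts a CTCAE grade 2 event in row 3.

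**2. Direction, single event.** Use the three-row mapping as an assumption. Of 3 × 5 = 15 possible pairs:

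- 5 agree;
- 7 have the maximum above the investigator rating;
- 3 have it above the CTCAE category;
- 0 have it above both.

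The total is 5 + 7 + 3 = 15. The maximum is never below either input.

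**3. Direction, participant.** For a participant with several events, the largest of the event-level maxima equals max(largest S, largest C). It is therefore always one of the two single-scale maxima. Enumerating all two-event combinations of the 15 pairs confirms that none exceeds both.

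**4. Direction, table total.** Totals behave differently. Take one participant whose only event is severe and grade 2, and another whose only event is moderate and grade 3. Each scale alone counts one participant in the top category; the maximum rule counts two. So a total can exceed both scales, but only when disagreements run in both directions.

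**5. Illustration of size (assumed rates).** SAP 7.3 and 8.5 close recruitment at 60, so about 30 per arm at 1:1. Let p be the proportion in the top category on each scale and k the share of those who are in it on both. Then

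proportion under the rule = p + p − kp = p(2 − k), and the ratio to either scale alone = 2 − k.

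With p = 10%, either scale alone gives 30 × 0.10 = 3.0 participants. Under the rule:

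| Overlap k | 30 × 0.10 × (2 − k) | Ratio |
|---|---|---|
| 100% | 3.0 | 1.00 |
| 75% | 3.75 | 1.25 |
| 50% | 4.5 | 1.50 |
| 25% | 5.25 | 1.75 |

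The ratio does not depend on p. If every severe event is also grade 3 or higher, the rule returns exactly the CTCAE count for that category. Neither p nor k is given in the documents.

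**The case against.** The strongest reply is that this is one descriptive table with no test or decision attached. The rule is the same in both blinded arms, and an upward-only rule cannot hide a severe event. SAP 9.8.1 also lists every event and tabulates serious TEAEs, TEAEs leading to death and TEAEs leading to permanent discontinuation, so a fatal event is visible whatever the severity rule. All of that stands, and it limits the consequence. It does not make the rule defined or supply a table on either protocol scale.

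A reader might infer two stronger things that the documents do not support.

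- *That the table necessarily overstates severity against both scales.* For any event or participant the value equals one of the two ratings (steps 2 and 3). Only totals can exceed both, and nothing in the documents shows in which direction ratings will disagree.
- *That the rule interferes with the stopping or termination criteria.* Protocol 4.5 and 4.6 act during the trial on individual CTCAE grades, in most cases together with relatedness, and not on an end-of-study table. Most of those triggers could not be checked even from a pure CTCAE table, because it carries no relatedness.

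The scope is also open to argument. Read literally, the sentence covers only events that recur in a participant. That narrows the rule, but it leaves unsaid how a participant with a single event is classified in the same table.

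Finally, it would be wrong to replace the three-level rating by CTCAE grade as the sole summary, since Protocol 8.4.3 plans a summary by severity and 9.4.1.4 defines that scale. The fix keeps both.

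**Conclusion.** The point holds as a defect in how the severity summary is specified. The SAP combines two unlike scales by a maximum that has no meaning until a mapping is given. Under any order-preserving mapping the result equals or exceeds each scale, so every disagreement is resolved upward. The only severity table listed would represent neither protocol scale, might merge grades 3, 4 and 5, and is an undeclared departure from Protocol 8.4.3. Single-occurrence events are left unclear.

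The size is unknown. The ratios of 1.00 to 1.75 rest on the assumed mapping, equal rates on the two scales and assumed overlaps of 100% down to 25%; at full overlap there is no inflation. Efficacy results, recorded data and the operation of the stopping and termination rules are untouched. It should be corrected because this is the sole severity summary and the correction is cheap.

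**What to change.** In SAP 9.8.1:

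1. Delete the parenthesis that combines the two ratings.
2. Tabulate TEAEs by SOC and PT and maximum investigator severity (mild, moderate, severe). This delivers the summary planned in Protocol 8.4.3.
3. Add a separate table of TEAEs by SOC and PT and maximum CTCAE grade (1 to 5).
4. State that each maximum is taken within one scale only and applies to every participant with a TEAE, whether the event occurred once or more often. Do not combine the scales.

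The cost is one SAP sentence and one additional table shell. The present rule already presupposes that both ratings are held, so no new data are needed, and no clinical rule changes.
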